3.1.1.3 Imaging

All imaging will be sent to the central imaging core laboratory for independent review as soon as possible within 48 hours of acquisition. Further instructions will be provided by the imaging core laboratory in separate guidelines.

Patients will undergo 4 types of imaging during the dose escalation phase: planar whole body (WB) scans, single photon emission computed tomography (SPECT)/CT scans, diagnostic CT scans, and brain MRI scans, as shown in [Table 1](#). Imaging to evaluate the organ/target lesion uptake will be performed after each CAM-H2 administration during the dose escalation phase of

the study for all patients at all dose levels. Dosimetry in tumor lesions, calculated based on consecutive SPECT/CT and planar WB scans, will be performed during Cycle 1. To evaluate disease progression, diagnostic CT scans will be performed in all patients, and brain MRI will only be performed in patients with known brain metastases. Patients with extracranial lesions will be evaluated for progression using RECIST version 1.1. Patients with brain metastases without extracranial lesions will be evaluated for progression using RANO-BM. Patients with extracranial lesions and brain metastases will be evaluated for progression using both RECIST version 1.1 (extracranial lesions) and RANO-BM (brain metastases). Additional details are provided in the Imaging Review Charter.

Table 1. Imaging During the Dose Escalation Phase

Type of Imaging	Cycle 1	Cycles 2, 3, and 4
Planar WB scans for PD distribution [1], evaluation of organ/target lesion uptake, and/or dosimetry	
After each dose (Dose 1 and Dose 2):
 
 • 5 hours (± 1 hour) after CAM-H2 [2]; • 24 hours (± 4 hours) after CAM-H2; • 48 hours (± 4 hours) after CAM-H2; and • 168 hours (± 24 hours) after CAM-H2. 	After each dose (Dose 1 and Dose 2): • 24 hours (± 4 hours) after CAM-H2 [2].
SPECT/CT scans to evaluate organ/target lesion uptake and/or dosimetry	
After each dose (Dose 1 and Dose 2):
 
 • 5 hours (± 1 hour) after CAM-H2; • 24 hours (± 4 hours) after CAM-H2; • 48 hours (± 4 hours) after CAM-H2; and • 168 hours (± 24 hours) after CAM-H2. 	NA

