3.1.2 Dose Expansion Phase

3.1.2.1 Screening

Following the completion of the dose escalation phase and determination of the MTD or RDP2, the study will be expanded so that a total of at least 52 patients will be exposed to the dose chosen to be taken forward. Of the included patients with advanced/metastatic breast cancer, at least 10 to 12 patients should have measurable brain metastases. The number of patients with gastric or GEJ cancer and brain metastases is not pre-set.

Patients will be screened for study eligibility over 2 different study visits (Visit 1 and Visit 2) in the 29 days prior to dosing (ie, Day -28 to Day 0 of Cycle 1). Visit 2 should occur preferably within the 14 days prior to study drug administration (Visit 3). All patients will undergo pre-treatment imaging for eligibility and baseline at Visit 1 with a diagnostic CT scan for RECIST version 1.1. Patients with known brain metastases will undergo a brain MRI scan, in addition to the diagnostic CT, for RANO-BM.

As in the dose escalation phase, the screening period may be extended up to an additional 2 weeks upon Sponsor approval in certain exceptional cases (eg, to allow for a repeat blood draw or to assess previously unavailable imaging results) following a discussion between the Principal Investigator, Medical Monitor, and Sponsor.

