4 SELECTION AND WITHDRAWAL OF PATIENTS

4.1 Inclusion Criteria

Patients who meet all of the following criteria will be eligible to participate in the study:

1. Informed consent form (ICF) signed voluntarily before any study-related procedure is performed, indicating that the patient understands the purpose of, and procedures required for, the study and is willing to participate in the study;
2. Males and females ≥ 18 years of age at screening;
3. ECOG PS of 0 to 1 (see [Appendix C](#));
4. HER2-positive locally advanced or metastatic breast cancer refractory to standard cancer treatment or HER2-positive locally advanced or metastatic gastric or GEJ cancer, refractory to standard cancer treatment;
5. Patients should have a minimum of 1 measurable lesion as defined by RECIST version 1.1 or a minimum of 1 measurable lesion as defined by RANO-BM within 4 weeks of the first dose of the study drug (Day 1). The lesion has to be a new lesion or progression of an existing lesion under the current therapy;
6. Any previous anti-HER2 treatment for advanced or metastatic disease is allowed. Patients with breast cancer should have had at least 2 previous systemic anticancer treatments for recurrent, locally advanced or metastatic cancer. Patients with gastric cancer or GEJ cancer should have had at least 1 previous anti-HER2 treatment;
7. Life expectancy >6 months;
8. Adequate organ function, determined by the following laboratory tests at screening:
 - Adequate kidney function with an eGFR of >59 mL/minute calculated using the Chronic Kidney Disease Epidemiology Collaboration equation;¹²
 - Adequate hepatic function defined as an ALT and AST $<2.5 \times$ ULN, or $<5 \times$ ULN in patients with liver metastases, and total bilirubin $<2 \times$ ULN;
 - Neutrophil count >1500 cells/mm³ without growth factor support (14 days after last pegylated granulocyte colony-stimulating factor or 7 days after regular granulocyte colony-stimulating factor);
 - Platelet count $>100,000$ cells/mm³ without platelet transfusion in the last 2 weeks;
 - Hemoglobin >9.0 g/dL without blood transfusion in the last 2 weeks; and
 - Adequate coagulation defined as an international normalized ratio (INR) ≤ 1.5 and activated partial thromboplastin time $<1.5 \times$ the upper limit of the institutional normal range;
9. Baseline left ventricular ejection fraction (LVEF) $\geq 50\%$ as measured by echocardiography or multigated acquisition scan;

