7 EFFICACY AND DOSIMETRY VARIABLES

7.1 Primary Efficacy Variables

The primary efficacy endpoints are as follows:

- Proportion of patients achieving an objective response (CR or PR) with the use of CAM-H2 as measured by RECIST version 1.1 (all patients with extracranial lesions) or as measured by RANO-BM (patients with brain metastases without extracranial lesions); and
- CBR of CAM-H2 using the equation $CBR = CR + PR + SD$, as measured by RECIST version 1.1 (all patients with extracranial lesions) or as measured by RANO-BM (patients with brain metastases without extracranial lesions).

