7.4 Efficacy Assessments

7.4.1 Objective Response

The proportion of patients achieving an objective response will be measured using RECIST version 1.1 (see [Appendix D](#)) or RANO-BM (see [Appendix E](#)). All patients with extracranial lesions will be evaluated for progression using RECIST version 1.1. Patients without extracranial lesions will be evaluated for progression using RANO-BM.

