APPENDIX D: TUMOR MEASUREMENTS AND THE RESPONSE EVALUATION CRITERIA IN SOLID TUMORS VERSION 1.1

Tumor measurements for Response Criteria in Solid Tumors (RECIST) version 1.1 are to be performed for all patients during screening as follows:

- All patients will undergo pre-treatment imaging for eligibility and baseline at Visit 1 with a diagnostic computed tomography (CT) scan for RECIST version 1.1.

Thereafter, tumor measurements and disease response assessments are to be performed as follows:

- Imaging to evaluate disease status after treatment will start 4 weeks after the last CAM-H2 infusion (Dose 2) of the cycle, at Week 8 (Visit 10 or Visit 19), and every 8 weeks thereafter, as long as there is no disease progression. For patients with disease progression, imaging to evaluate disease status will be performed according to the local site standard of care).

During screening, tumor lesions are to be categorized as measurable versus non-measurable and target versus non-target, as follows:

Measurable versus non-measurable

- Measurable: Measurable disease is defined as:
 - Lesions that can accurately be measured in at least 1 dimension (the longest diameter in the plane of measurement to be recorded) with a size ≥ 10 mm by CT scan; and
 - Malignant lymph nodes ≥ 15 mm in short axis when assessed by CT scan. At baseline and in follow-up, only the short axis will be measured and followed.
- Non-measurable: Non-measurable disease is defined as all other lesions, including small lesions (longest diameter < 10 mm or pathological lymph nodes with ≥ 10 to < 15 mm short axis), and truly non-measurable lesions.

Target versus non-target

- Target: Target lesions will include all measurable lesions up to a maximum of 2 lesions per organ and 5 lesions in total, representative of all involved organs. Target lesions are to be selected on the basis of their size (ie, those with the longest diameter) and suitability for accurate repeated measurement. Lymph nodes may be selected as target lesions; they must be defined as measurable, and only the short axis of the node will contribute to the baseline sum. All other pathologic nodes with short axis ≥ 10 mm but < 15 mm should be considered non-target lesions; and
- Non-target: All other lesions not classified as target lesions (or sites of disease) are to be identified as non-target lesions and are to be recorded in the electronic case report form. Measurement is not required.

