Disease response in target and non-target lesions will be assessed by the Investigator using RECIST version 1.1, according to the categories and criteria described in [Table 12](#) below.

Table 12. Response Evaluation Criteria in Solid Tumors Version 1.1 Guidelines

Disease Response Criteria for Target and Non-Target Lesions	
Evaluation of Target Lesions	
CR	Disappearance of all target lesions. Any pathologic lymph nodes (whether target or non-target lesions) must have a reduction in SAD to less than 10 mm.
PR	At least a 30% decrease in the SOD (LD for non-nodal lesions and SAD for nodal lesions) of target lesions, taking as reference the baseline sum diameters.
SD	Neither sufficient shrinkage to qualify for PR nor sufficient increase to qualify for PD, taking as reference the smallest sum diameters since the treatment started.
PD	At least 20% increase in the sum of the diameters of target lesions, taking as reference the smallest sum on study (this includes the baseline sum if that is the smallest sum on study). In addition to the relative increase of 20%, the sum must also demonstrate an absolute increase of at least 5 mm (Note: the appearance of 1 or more new lesions is also considered progression).
Evaluation of Non-Target Lesions	
CR	Disappearance of all non-target lesions and normalization of tumor marker level.
Non-CR/Non-PD	Persistence of 1 or more non-target lesion(s) or/and maintenance of tumor marker level above the normal limits.
PD	Appearance of 1 or more new lesions and/or unequivocal progression of existing non-target lesions.

CR = complete response; LD = longest diameter; PD = progressive disease; PR = partial response; SAD = short axis diameters; SD = stable disease; SOD = sum of the diameters.

Source: Eisenhauer EA, Therasse P, Bogaerts J, et al. New response evaluation criteria in solid tumours: revised RECIST guideline (version 1.1). *Eur J Cancer*. 2009;45(2):228-247

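### Primary ORR and CBR choose RECIST or RANO-BM by the presence of any extracranial lesion, not by where disease is measurable, so some patients who enter on a brain lesion may have no target lesion to score

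*Combined protocol and SAP*

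**What the plan says.** **Entry.** Inclusion criterion 5 (section 4.1) asks for "a minimum of 1 measurable lesion as defined by RECIST version 1.1 or a minimum of 1 measurable lesion as defined by RANO-BM". Either compartment is enough, and nothing excludes non-measurable extracranial disease alongside a measurable brain lesion.

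**Primary endpoints.** Section 7.1 defines ORR and CBR "as measured by RECIST version 1.1 (all patients with extracranial lesions) or as measured by RANO-BM (patients with brain metastases without extracranial lesions". Section 7.4.1 repeats the split: "All patients with extracranial lesions will be evaluated for progression using RECIST version 1.1. Patients without extracranial lesions will be evaluated for progression using RANO-BM". Neither mentions measurability. Section 7.4.2 says that CBR uses both sets of criteria, then gives the same either/or allocation.

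**Scope of each set of criteria.** Section 3.1.1.3 says that patients with disease in both sites "will be evaluated for progression using both RECIST version 1.1 (extracranial lesions) and RANO-BM (brain metastases". The synopsis and sections 3.1.3 and 6.5 say the same. All of these concern progression.

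**RECIST categories.** In Appendix D, "Target lesions will include all measurable lesions up to a maximum of 2 lesions per organ and 5 lesions in total", and "Non-measurable disease is defined as all other lesions, including small lesions". Table 12 lists PR and SD under target lesions only. Non-target disease can be CR, PD or Non-CR/Non-PD, the last defined as "Persistence of 1 or more non-target lesion(s) or/and maintenance of tumor marker level above the normal limits".

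**Denominator and recruitment.** Section 9.1 analyses efficacy in the FAS, which is every dosed patient; there is no measurable-disease or response-evaluable set. In the expansion breast population, "at least 10 to 12 patients should have measurable brain metastases" (section 3.1.2.1).

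**The concern.** Eligibility follows measurable disease, but the primary read follows the mere presence of an extracranial lesion. A patient can therefore be admitted on a brain metastasis and then be scored by criteria that do not read it. Shrinkage of that lesion by 30% or more would not make the patient a responder. A patient who is simply not progressing would be Non-CR/Non-PD, which is not a term in CBR = CR + PR + SD.

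The loss would fall on patients with measurable brain metastases, whom the expansion deliberately recruits. It would act mainly downward on both primary efficacy endpoints. It can also mislead upward: disappearance of a small extracranial nodule could be recorded as CR while the qualifying brain lesion persists. If the ORR below 10% rule in section 9.2.4 uses the same allocation, one uncounted responder could decide whether an indication continues.

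**Working it through.** The protocol gives no figure to reproduce here: the 52 patients come without a formal calculation (section 9.2.4). The check is a trace of one patient type, followed by sizing under stated assumptions.

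**Trace.** Take an illustrative patient with a 20 mm contrast-enhancing brain metastasis, adequately visible on MRI, and an 8 mm lung nodule.
1. Section 4.1, criterion 5: measurable by RANO-BM, so this criterion is met.
2. Sections 7.1 and 7.4.1: an extracranial lesion is present, so RECIST 1.1 applies.
3. Appendix D: the nodule is under 10 mm, so it is non-measurable and cannot be a target. A lymph node of 12 mm short axis would fare the same, because nodes need 15 mm.
4. If RECIST covers extracranial lesions only, there is no target lesion. Table 12 then leaves CR, Non-CR/Non-PD or PD.
5. Section 7.1: Non-CR/Non-PD is not in the CBR sum, and the protocol nowhere maps it to SD.
6. Section 9.1: the patient remains in the denominator.

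**Effect on the final estimates.** Let m be the number of such patients among 52. The documents do not give m; assume 1 to 4. Assume a 30% PR rate and 60% disease control in these patients, and ignore CR.

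- ORR loss = m × 0.30 / 52. For m = 1: 0.3/52 = 0.6 points. For m = 4: 1.2/52 = 2.3 points.
- CBR loss = m × 0.60 / 52. For m = 1: 0.6/52 = 1.2 points. For m = 4: 2.4/52 = 4.6 points.

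For scale, the 95% half-width for a 30% rate at n = 52 is 1.96 × √(0.30 × 0.70 / 52), about 12 points.

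**Effect on the interim, if it uses the same allocation.** The number of responders needed to avoid the rule is r, the smallest whole number at or above 0.10 × n. This gives r = 1 at n = 10 (the decision turns on 0 versus 1), r = 2 for n = 11 to 20 (1 versus 2), and r = 3 at n = 26. The chance of ORR below 10% is P(Binomial(n − m, p) < r), where m is now the number at the interim who cannot score PR. The interim n per indication is not given. With an assumed true ORR of p = 0.20:

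| Assumed n | r | m = 0 | m = 1 | m = 2 | m = 3 |
|---|---|---|---|---|---|
| 13 | 2 | 23.4% | 27.5% | 32.2% | 37.6% |
| 20 | 2 | 6.9% | 8.3% | 9.9% | 11.8% |
| 26 | 3 | 8.4% | 9.8% | 11.5% | 13.3% |

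Example for n = 20:
- m = 0: 0.8^20 + 20 × 0.2 × 0.8^19 = 0.0115 + 0.0576 = 0.069.
- m = 3: 0.8^17 + 17 × 0.2 × 0.8^16 = 0.0225 + 0.0957 = 0.118.

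If 1 to 4 patients are affected in all, about 0.5 to 2 would be expected by the halfway point, so m = 3 is a high case.

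**The case against.** The strongest reply is that the text does not settle the outcome, and much of that stands.

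- A reader might infer that these patients certainly cannot be PR or SD. The documents do not go that far. Appendix D never bars a brain lesion from being a RECIST target, and the restriction of RECIST to extracranial lesions is written for progression, not response. Against this, sections 3.1.1.1 and 3.1.2.1 obtain the brain MRI for RANO-BM, so the restricted reading is the natural one.
- A reader might treat the CBR loss as fixed. The opening of section 7.4.2 would make a RANO-BM result available for CBR; its own next sentences then restore the either/or split. That is a conflict, not an answer.
- A reader might conclude that the interim ORR is biased as written. Section 9.2.4 names both sets of criteria without the extracranial allocation, so the effect there is conditional.
- A reader might also conclude that affected patients would be refused a further cycle. No section ties that decision to the allocation in section 7.1; Cycle 2 eligibility rests on disease state and safety (sections 6.2.2.9 and 6.3.2.9).
- The Imaging Review Charter, to which detail is deferred, is not in the documents and may map Non-CR/Non-PD to an overall response. Even so, the definition of a primary endpoint belongs in the protocol.

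The subgroup may also be small: the extracranial status of the patients with brain metastases is not stated.

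**Conclusion.** The point holds as a defect in the endpoint definition. The stated allocation can leave a patient who entered on a brain lesion with no lesion on which PR or SD can be scored, while keeping that patient in the denominator. This depends on reading RECIST on extracranial lesions only, which the protocol supports for progression but does not state for response. Sections 7.1, 7.4.1 and 7.4.2 and Appendix D need to be reconciled.

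Under the assumptions above, the average bias is modest: at most 2.3 points of ORR and 4.6 points of CBR, well inside the sampling error. The interim is the more sensitive place, and only if it uses the same allocation. The number affected, the response rates and the interim size are all assumptions; the trace does not depend on them. The change should be made because it is cheap and concerns both primary efficacy endpoints.

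**What to change.** In the synopsis, sections 2.1, 7.1, 7.4.1 and 7.4.2, and the interim rule in section 9.2.4:

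1. Assign the primary response criteria by site of measurable disease: RECIST 1.1 if there is at least one RECIST-measurable extracranial lesion; RANO-BM if the only measurable disease is in the brain.
2. In the RANO-BM group, follow extracranial lesions as non-target. Their unequivocal progression, or a new extracranial lesion, counts as PD. Their persistence precludes an overall CR, so the best overall response is PR.
3. State that brain lesions are not RECIST targets.
4. Count Non-CR/Non-PD with SD in CBR for any patient without target lesions.
5. Remove the conflict in section 7.4.2 between using both sets of criteria and using one or the other.

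Reconcile the passages on clinical benefit for a further cycle with this scoring; no clinical rule is proposed here.

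The cost is protocol wording and alignment of the Imaging Review Charter. CT and MRI are already planned for patients with known brain metastases. Slightly more patients would be read by RANO-BM, whose CR and PR must be sustained for at least 4 weeks (Appendix E, Table 13). Table 12 states no such requirement, so the difference should be acknowledged when the results are pooled.

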7.2 Secondary Efficacy Variables

The secondary efficacy endpoints are as follows:

- PFS for patients receiving CAM-H2;
- DoR in patients receiving CAM-H2;
- PFS in patients with brain metastases receiving CAM-H2;
- OS for patients receiving CAM-H2; and
- Proportion of patients on CAM-H2 who develop ADAs.

7.3 Dosimetry Variables

The dosimetry endpoint consists of dosimetry for CAM-H2 via SPECT/CT and planar WB scans. Endpoints will include the biodistribution and PD profile of CAM-H2 dosimetry results for target lesions based on region of interest.

7.4 Efficacy Assessments

7.4.1 Objective Response

The proportion of patients achieving an objective response will be measured using RECIST version 1.1 (see [Appendix D](#)) or RANO-BM (see [Appendix E](#)). All patients with extracranial lesions will be evaluated for progression using RECIST version 1.1. Patients without extracranial lesions will be evaluated for progression using RANO-BM.

7.4.2 Clinical Benefit Rate

The CBR will be measured using the equation $CBR = CR + PR + SD$, as measured by both RECIST version 1.1 (see [Appendix D](#)) and RANO-BM (see [Appendix E](#)). All patients with extracranial lesions will be evaluated for progression using RECIST version 1.1. Patients without extracranial lesions will be evaluated for progression using RANO-BM.

7.4.3 Additional Clinical Measurements of Efficacy

In addition to objective response and CBR, the clinical measurements of efficacy evaluated will include PFS, DoR, and OS.

7.4.4 Anti-Drug Antibodies

Blood samples for ADAs will be collected per the laboratory manual instructions. ADAs will be measured during the study via serum sampling using a validated method.

7.4.5 Exploratory Biomarkers

Blood samples for exploratory biomarkers will be collected from patients who have consented to the procedure. The samples will be collected per the laboratory manual instructions and stored at the central laboratory for future analyses. The analyses of these exploratory biomarkers will be performed outside of the scope of this study protocol and will be reported separately.

7.4.6 Dosimetry Study Procedures

For the dosimetry study, defined critical organs (ie, the kidneys and liver) and target lesions (ie, lesions representative of the extent of disease and deemed avid at the discretion of the central reviewer, based on qualitative visual assessment) will be delineated on planar WB scans and/or SPECT/CT scans. Further details are provided in the Imaging Review Charter.

The percentage of injected activity (%IA) will be calculated in each set of images as the ratio between the measured activity in the lesion and the total injected activity as a function of time to derive the absorbed dose. Organ time-activity curves will be generated by plotting %IA versus time to derive the absorbed dose.

Tumor dosimetry in tumor lesions will be calculated based on the consecutive SPECT/CT and/or planar WB scans during Cycle 1 of the dose escalation phase.

8 SAFETY ASSESSMENTS

Safety and tolerability will be assessed during the study and will include the following:

- Incidence and severity of treatment-emergent adverse events (TEAEs);
- MTD of CAM-H2;
- DLT rate of CAM-H2;
- RDP2 for CAM-H2;
- Physical examinations, including full neurologic examinations, as well as assessments of general appearance, skin, eyes, ears, nose, throat, neck, lymph nodes, chest, heart (including auscultation for heart sounds and murmurs), abdomen, extremities, and musculoskeletal systems;
- Vital signs, including systolic and diastolic blood pressure, heart rate, respiratory rate, and temperature;
- Clinical laboratory tests including thyroid panel (thyroid-stimulating hormone [TSH], free T4, and free T3), hematology assessments (white blood cell [WBC] count and differential, hemoglobin, hematocrit, and platelet count), coagulation parameters (activated partial thromboplastin time, INR, and prothrombin time), and chemistry assessments (fasting glucose or glycated hemoglobin, creatinine, blood urea nitrogen, sodium, potassium, calcium, chloride, phosphorus, bicarbonate, AST, ALT, gamma-glutamyl transferase [GGT], alkaline phosphatase, total bilirubin [or fraction of direct bilirubin if $>1.5 \times \text{ULN}$], albumin, total protein, lactate dehydrogenase [LDH], creatine kinase (CK) [or fraction of creatine kinase-myocardial band (CK-MB) if $>1.5 \times \text{ULN}$], and cystatin-C);
- Urinalysis for kidney biomarkers (including kidney injury molecule-1 [KIM-1], neutrophil gelatinase-associated lipocalin [NGAL], microalbumin, creatinine, and albumin/creatinine ratio) and for microscopic evaluation of sediment (including cylinders, erythrocytes, and leukocytes);
- Pregnancy test (including serum and urine testing);
- Dosimetry results with regard to estimated absorbed dose to the most exposed organs (ie, the kidneys and liver); and
- Concomitant medications.

